The studies described above are observational and so far no randomized clinical trial has been published evaluating the efficacy of NIFC to improve the identification of the extra-hepatic biliary structures. Additionally it would be relevant to investigate the ability of the NIFC to reduce intraoperative bleeding, duration of laparoscopic cholecystectomy. Further, it is central to assess whether NIFC can improve the outcomes in some subpopulation of patients for whom the evaluation and dissection of the Calot's triangle is difficult, e.g. obese patients or patients undergoing inflammatory processes. Finally, the potential use of NIFC as a training tool in laparoscopic surgery is still to be studied.

c. Strengths and Limitations

The strength of the study is the ability to investigate whether the extra-hepatic biliary tract is more visible using NIFC when compared with white light (WLI) alone. It is a multicenter study with diverse patient populations and surgeons from different countries/continents that will validate this method globally.

Limitations may include impossibility to randomize by surgeon.

3. Study Overview

The Study is designed to compare the effectiveness of Near Infrared Fluorescence Cholangiography (NIFC) to standard white light imaging (WLI) in visualizing and identifying the main biliary and hepatic structures (Cystic Duct, Right Hepatic Duct, Common Hepatic Duct, Common Bile Duct, Cystic-CBD junction, Cystic-Gallbladder junction and any Accessory Ducts) during laparoscopic cholecystectomy.

4. Study Objectives

a. Primary Objective:

Multi-center Study Protocol: Efficacy of Near Infrared Incisionless Fluorescent Cholangiography (NIFC) during Laparoscopic Cholecystectomy

Demonstrate that NIFC performs better than standard white light (WLI) alone in visualizing and identifying extra-hepatobiliary structures (Cystic Duct, Right Hepatic Duct, Common Hepatic Duct, Common Bile Duct, Cystic-CBD junction, Cystic-Gallbladder junction, and any Accessory Ducts) before and after dissection during Laparoscopic Cholecystectomy (LC).

b. Secondary Objectives:

1. Demonstrate that NIFC is an effective teaching tool to assist students and residents present in the O.R. during the procedure to identify extra-hepatobiliary structures (before/after dissection).
2. Demonstrate that the Time to Clip, which is defined as the time from the moment Calot's Triangle is first visualized to when the clip is applied, is reduced when using NIFC vs WLI alone.

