3. Compare the mean number of procedures that required Conversion to Open using NIFC vs WLI alone.
4. Compare the mean Volume of Bleeding using NIFC vs WLI alone.
5. Compare the Incidence rate of Bile Leakage from the liver bed using NIFC vs WLI alone.
6. Compare the Incidence rate of Bile Duct Injury (BDI) using NIFC vs WLI alone.
7. Compare the mean Surgeon Confidence Level using NIFC vs WLI alone.

5. Study Endpoints

a. Primary Endpoint:

Detection Rate (DR) of each particular extra-hepatobiliary structure during Laparoscopic Cholecystectomy (LC) defined as the total number of patients in which the particular structure is detected before and after dissection in that arm of the Study (WLI or NIFC), divided by the total number of patients in that arm. Extra-hepatobiliary structures to be included in this assessment: Cystic Duct, Right Hepatic Duct, Common Hepatic Duct, Common Bile Duct, Cystic-CBD junction, Cystic-Gallbladder junction, and any Accessory Ducts.

b. Secondary Endpoints:

1. The DR for students/residents only (apart from experienced surgeons), both before and after dissection.
2. Time to Clip
3. Incidence of Conversion to Open Surgery
4. Volume of Bleeding
5. Incidence of Bile Leakage from the liver bed
6. The mean Incidence of Bile Duct Injury (BDI)
7. Surgeon Confidence Level

6. Covariates

Besides the comparison of the outcomes in both study arms, we will conduct an exploratory analysis to identify potential effect modifiers. The following baseline variables will be considered:

- 1) Patient data:
 - a) Age
 - b) Gender
 - c) BMI
- 2) Patient history/condition:
 - a) obesity
 - b) liver disease
 - c) lithiasis
 - d) surgery status (elective/urgent/emergent)
- 3) Intra-operative factors:
 - a) amount of fat covering cystic artery
 - b) amount of inflammation
 - c) presences of adhesions / scar tissue
- 4) Surgeon expertise (resident/attendant)

7. Additional Observations (NIFC group only)

a. “Reflux Maneuver”

According to previous publications, in some cases the Cystic Duct may not be seen with NIFC because the Cystic Duct may not contain ICG at the time of viewing. In those cases, a “reflux maneuver” [defined as using an atraumatic laparoscopic instrument to push on the Common Bile Duct in order to move more of the ICG from the Common Bile Duct through the Cystic Duct into the Gallbladder – thereby increasing visualization of the Cystic-Gallbladder junction] can be performed.

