We will evaluate the usefulness of the Reflux Maneuver to visualize the Cystic Duct.

8. Design

a. Study Population

Participants will include patients aged 18-years old and above selected for Laparoscopic Cholecystectomy (LC).

b. Setting(s)

Participants will be recruited by the Department of Surgery at the following study sites, all of which are recognized hepato-bilio-pancreatic surgery centers:

- Cleveland Clinic (Weston, FL, USA)

Multi-center Study Protocol: Efficacy of Near Infrared Incisionless Fluorescent Cholangiography (NIFC) during Laparoscopic Cholecystectomy

- Cleveland Clinic (Cleveland, OH, USA)
- Cedars-Sinai Medical Center (Los Angeles, CA, USA)
- Hospital de Clínicas José de San Martín (Buenos Aires, Argentina)
- Tokyo Medical University Hospital (Tokyo, Japan)
- Asklepios Westklinikum (Hamburg, Germany)
- University of Insurbia (Varese, Italy)
- Klinikum Südstadt Rostock (Rostock, Germany)
- Kliniken Essen-Mitte (Essen, Germany)

Surgeons trained in laparoscopic and hepato-bilio-pancreatic (HBP) surgery will participate in the study. Principal and Lead Site Investigators of this Protocol are seniors and recognized HBP surgeons. Additionally, junior surgeons will be involved in the study. When a resident is present in the OR, he/she will perform the procedure under the supervision of the senior surgeon.

c. Enrollment Process

Eligible patients will be identified through clinical and test evaluation. Eligibility will be verified by the patient's primary surgeon. The surgeon will determine the indication and date of the surgery. Once a patient is confirmed as eligible, the surgeon will introduce the study in detail. If after being introduced to the study and having had the opportunity to ask questions, the patient is willing to participate, he/she will be asked to review and sign the informed consent document (Appendix XXX).

Upon entry in the clinical trial patients will be randomly allocated to the intervention arm. Data will be collected at enrolment time, during surgery, at the end of surgery and one week after surgery.

d. Randomization Process

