Upon entry in the clinical trial, the master study database (REDCap, described later in Section 16) will randomly allocated patients to one of the study arms (1:1) within site (1:1) using a computer generated random sequence. This will provide an allocation sequence for each site. Once a patient is enrolled and a database file in REDCap is initiated for that patient, he/she will be assigned electronically to one of the study arms.

Patient will be blind to the intervention but surgeon blinding will not be feasible due to the nature of the intervention. The study will involve a considerable number of surgeons in each site, which should compensate any potential bias of some of them in favor or against either approach.

e. Flow chart

Multi-center Study Protocol: Efficacy of Near Infrared Incisionless Fluorescent Cholangiography (NIFC) during Laparoscopic Cholecystectomy

[figure not shown]
Figure 1 shows the flow chart for the study, a multi-centered randomized controlled trial (RCT) 1:1 with two arms:

1. Control: WLI

A laparoscopic cholecystectomy will be performed using Xenon white light imaging (WLI) only.

2. Experimental: NIFC

A laparoscopic cholecystectomy will be performed using both white light imaging and near infrared light imaging with indocyanine green (ICG) intravenous dye.

9. Data collection and procedures

Data will be collected before, during and at the end of surgery; and one week after surgery.

a. Pre-Op data collection

i. Patient data

- Age
- Gender
- Weight
- Height
- BMI

ii. Patient clinical characteristics

- Liver disease
- Lithiasis
- Surgical status: elective/urgent/emergent

b. Intra-Op data collection

i. For NIFC arm only

- Time of ICC administration
- Was there any Adverse Reaction? If so, what happened and how was the patient treated?

ii. For both arms: PRIOR to dissection

- Categorize initial visualization
 - Amount of fat
 - Amount of inflammation
 - Presence of adhesions / scar tissue
- Remove the fat from the Calot's triangle area, retract the gallbladder and Hartmann's pouch
- Surgeon/Observer documents which extra-hepatic biliary structures are identified without doubt
- Start Dissection. Document the time hilar dissection was begun (baseline time)

iii. For both arms: AFTER dissection

- Surgeon/Observer documents which extra-hepatic biliary structures are identified without doubt
- Time to Clip: Document the time the Cystic Duct was clipped
- Volume of Bleeding
- Incidence of Bile Leakage

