2. PRE-DISSECTION

A. Categorize the initial visualization:

- Amount of fat: Can you see the Cystic Artery? Yes No
- Level of inflammation: Minimal Moderate Significant
- Were adhesions and/or scar tissue needed to be removed prior to visualization? Yes No

B. Remove the fat from the Calot's triangle area, retract the gallbladder and Hartmann's pouch.

C. Document visualization of extra-hepatic biliary anatomy:

For both arms, scope the Calot's triangle area using STD (white-light) mode. If in the NIFC arm, toggle between STD and ICG modes on light source as needed. Check the appropriate boxes below based on what is visible:

Time of Initial Visualization: _____ AM / PM

	Yes	Maybe	No
Cystic Duct			
Right Hepatic Duct			
Common Hepatic Duct			
Common Bile Duct (CBD)			
Cystic-CBD junction			
Cystic-Gallbladder junction			
Accessory Ducts			

D. For NIFC Arm Only: "Reflux Maneuver" Attempted? Yes No
If the Cystic Duct cannot be visualized with fluorescence, use anatraumatic laparoscopic instrument to push on the Common Bile Duct in order to move more of the ICG from the Common Bile Duct through the Cystic Duct into the Gallbladder – thereby increasing visualization of the Cystic Duct - Gallbladder Union. Check the appropriate boxes based on what is visible:

	Yes	Maybe	No
Cystic Duct			
Cystic-CBD junction			
Cystic-Gallbladder junction			

MULTICENTER TRIAL

Page 1 of 2

SURG-CRF v1.0

Multi-center Study Protocol: Efficacy of Near Infrared Incisionless Fluorescent Cholangiography (NIFC) during Laparoscopic Cholecystectomy

Near Infrared Incisionless Fluorescent Cholangiography (NIFC)
INTRA-OPERATIVE CASE REPORT FORM - PERFORMING SURGEON

START DISSECTION: Time of hilar dissection: _____ AM / PM

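### Fat, inflammation and adhesions are listed as baseline effect modifiers, but the unblinded surgeon grades them after allocation, so their interactions with arm should be descriptive only

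*Combined protocol and SAP*

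**What the plan says.** Section 6 states that "we will conduct an exploratory analysis to identify potential effect modifiers" and then says "The following baseline variables will be considered". The list mixes age, gender, BMI, obesity, liver disease, lithiasis and surgery status with a group that the protocol itself heads as intra-operative (fat over the cystic artery, inflammation, adhesions or scar tissue) and with surgeon expertise. Section 13.b fits regression models with covariates to see whether patient or surgeon characteristics and site modify the effect. It draws no line between variables that precede allocation and variables that follow it.

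On timing, Section 8.d says "Once a patient is enrolled and a database file in REDCap is initiated for that patient, he/she will be assigned electronically". On masking, the same section says that "surgeon blinding will not be feasible due to the nature of the intervention".

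On measurement, Section 9.b.ii files the three factors under intra-operative data. Only the performing surgeon's form (Appendix d, item 2.A) collects them. Fat is a yes/no item, "Amount of fat: Can you see the Cystic Artery"; inflammation has three levels without criteria; adhesions are a yes/no on whether removal was needed.

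On use, Section 2.b says "it is central to assess whether NIFC can improve the outcomes in some subpopulation of patients", with obese patients and inflammatory processes as its examples. On the operator, Section 8.b says "When a resident is present in the OR, he/she will perform the procedure under the supervision of the senior surgeon".

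**The concern.** A subgroup analysis of a randomised trial compares like with like only if subgroup membership cannot depend on arm. That holds for a variable that describes the patient before allocation. It is not guaranteed for one graded afterwards by someone who knows the arm. If surgeons grade difficulty differently in the two arms, the 'difficult' patients on NIFC and the 'difficult' patients on WLI are different kinds of patient. The within-stratum contrast then mixes the device effect with the change in case mix.

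At stake are statements about whether NIFC works differently in inflamed, fatty or adherent fields. The rationale gives weight to the first of these. The label 'baseline' would lead a reader of the results to give them the same standing as a BMI subgroup.

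**Working it through.** **1. Order of events in the documents.**
- Allocation: when the REDCap file is opened at enrolment (8.d).
- Arm known and acted on before the first incision: ICG is given in the NIFC arm at least 45 minutes ahead of surgery (12.c.ii, step 1).
- Grading of the three factors: item 2.A of the surgeon's form, which carries the study arm at its head. Item 2.A names no light mode.
- Detection call: item 2.C of the same form, by the same person.
- Completion: the form need only be finished before leaving the operating room (12.c.i step 6; 12.c.ii step 7), so 2.A can be entered after detection is known.
- Second rating: none. The observer form (Appendix e) has no fat, inflammation or adhesion item.
- Operator: the pre-operative form (Appendix c) has no operator field; operator details first appear on the intra-operative forms.

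**2. The plan's own figure.** The plan gives none for interactions. The table in 13.a sizes only the main comparison. At 500 per arm, one-sided 5%, it reproduces with power of 89.3% to 94.4%. It is not in dispute here.

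**3. What arm-dependent grading can do, independent of outcome.** Assumptions, none from the documents: 40% of patients truly difficult; WLI detection 40% (difficult) and 70% (easy); NIFC 50% and 80%, a true gain of 10 points in both. Let *d* and *e* be the true rates in one arm and *m* the share misgraded in that arm only.
- Easy graded as difficult: 'difficult' rate = (0.4d + 0.6me)/(0.4 + 0.6m).
- Difficult graded as easy: 'easy' rate = (0.6e + 0.4md)/(0.6 + 0.4m).

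Example, NIFC, m = 0.10: (0.4×0.50 + 0.06×0.80)/0.46 = 53.9%, so the gain is 53.9 − 40 = 13.9. Example, WLI, m = 0.10: (0.4×0.40 + 0.06×0.70)/0.46 = 43.9%, so the gain is 50 − 43.9 = 6.1.

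| Misgrading (m = 10% / 15%) | Gain in 'difficult' | Gain in 'easy' | OR ratio, difficult/easy |
|---|---|---|---|
| None | 10 | 10 | 0.875 |
| NIFC, easy to difficult | 13.9 / 15.5 | 10 | 1.024 / 1.092 |
| NIFC, difficult to easy | 10 | 8.1 / 7.3 | 0.980 / 1.029 |
| WLI, easy to difficult | 6.1 / 4.5 | 10 | 0.745 / 0.698 |
| WLI, difficult to easy | 10 | 11.9 / 12.7 | 0.801 / 0.771 |

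The last column matters because 13.b plans logistic or generalised mixed models. With no misgrading the odds ratios are (0.5/0.5)/(0.4/0.6) = 1.50 and (0.8/0.2)/(0.7/0.3) = 1.71, ratio 0.875. An equal gain in points is therefore already an interaction on the logit scale. NIFC-arm misgrading moves the ratio to about 1; WLI-arm misgrading moves it further below 1.

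**4. Grading that depends on the outcome.** Other assumptions: 30% difficult; control detection 30% in difficult cases and 50% overall, so (0.50 − 0.3×0.3)/0.7 = 58.6% in easy cases; a true gain of 10 in both. Suppose a share *u* of easy NIFC cases is graded difficult only when the structure was not seen. The NIFC rates become 0.12/(0.3 + 0.7×0.314u) in 'difficult' and 0.686/(0.686 + 0.314(1 − u)) in 'easy'. For u = 5/10/20/30% the gains are 8.6 v 11.1, 7.3 v 12.2, 4.9 v 14.6 and 2.8 v 17.1 points. On the risk-difference scale (Wald, two-sided 5%, 500 per arm) the false-positive interaction rate is 6.7/12.0/33.5/63.5%, against 5.0% with no misgrading. With outcome-independent upgrading of 5/10/20% of easy NIFC cases on these inputs, the gains are 13.0/15.4/19.1 v 10 and the rate is 7.5/13.4/30.1%.

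**5. Would tabulating 2.A by arm catch it?** On the step 3 inputs, the share graded difficult in the affected arm becomes 0.4 + 0.6m = 46% or 49%, or 0.4 − 0.4m = 36% or 34%, against 40%. Normal-approximation power for two proportions at 500 per arm, two-sided 5%, is about 48%, 82%, 26% and 50%.

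**The case against.** The strongest reply is that the plan is modest and its sequence already protective. Section 6 calls the analysis exploratory and openly heads the three factors as intra-operative. Sections 9.b.ii and form item 2.A place the grading before the structure check, adhesions are taken down under white light in both arms, and toggling to ICG mode first appears at the structure check. All of this stands, and it limits contamination by the fluorescent image. It does not remove the surgeon's knowledge of the arm, and no instruction fixes the light mode or the moment of recording. Section 8.d relies on having many surgeons to offset individual bias, but averaging does not remove a tendency shared by surgeons who all know the arm.

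A reader might infer that the bias must favour a finding that NIFC helps more in difficult anatomy. The documents do not support a direction: steps 3 and 4 give either sign, and the NIFC-arm signal nearly vanishes on the planned logit scale.

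A reader might also infer that the operator is chosen in the operating room once the arm is known. Section 8.b says only that a resident who is present operates. Nothing shows that presence depends on arm.

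Nor is the whole subgroup rationale undermined: obesity, one of its two examples, rests on pre-operative data. The fat item need not be replaced either. It asks about the artery that Section 6 names, and that artery is not one of the seven outcome structures.

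**Conclusion.** The point holds in limited form. Fat, inflammation and adhesions are post-randomisation ratings by an unblinded assessor who also scores the outcome, and the plan treats them as baseline effect modifiers. Arm-dependent grading could create or mask an interaction, in an unknown direction and of unknown size. Every figure in steps 3 to 5 rests on assumed prevalences, detection rates and misgrading shares, and shows only that modest misgrading can matter. The comparison between arms and the BMI/obesity subgroup are not touched. For operator level, the supported statement is only that it is not recorded before allocation. This is a worthwhile, inexpensive correction to an exploratory analysis and does not threaten the trial's main conclusion.

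**What to change.** - In Sections 6 and 13.b, label the three intra-operative factors as post-randomisation and report their interactions with arm as descriptive only.
- Base effect-modification statements on variables recorded pre-operatively: age, gender, BMI/obesity, lithiasis and surgery status. (Liver disease is also listed, but known liver disease is an exclusion criterion.)
- State that operator level is not fixed or recorded before allocation, so that its interaction is read with that in mind.
- In Section 12.c and on the surgeon's form, require item 2.A to be graded in STD mode and recorded before any ICG-mode viewing, in both arms.
- Tabulate 2.A by arm as a partial check only. Given the power in step 5, balance does not show that grading was unbiased, and the relabelling should not depend on it.

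The cost is SAP wording and one form instruction. The downside is that intra-operative subgroup results carry less weight.

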c. Patient Randomization

Each surgeon will follow the standard laparoscopic surgical protocol of his/her center, and will comply with the following additional steps according to which arm of the study the patient is assigned:

i. Control arm (WLI only) procedures

1. After inserting the scope in the abdominal cavity, once other standard operatory procedures (e.g., taking down adhesions if necessary, or releasing scar tissue) are completed using white light imaging (WLI) only, the Researcher will record the time when Calot's triangle is first visualized. From this moment on, the surgery will be recorded.
2. After removing the fat from the gallbladder area, lifting the gallbladder over the liver, and grabbing the Hartman's pouch to visualize the Calot's triangle, but PRIOR TO DISSECTION, the Researcher will determine what extra-hepatic biliary structures can be specifically identified. Of note: because one of the goals of the Study is to evaluate NIFC as a teaching tool, residents and juniors should record what structures they were able to identify by themselves before any intervention of the attendant surgeon.
3. Then, AFTER DISSECTION, a similar assessment of what extra-hepatic biliary structures can be specifically identified using WLI only will be performed.
4. Anatomic anomalies of the biliary system will be documented on the case form and if an anatomic variation is found, a snap shot photo will be taken in addition to the video.
5. Immediately before clipping or proceeding with open surgery, the total time from Step 1 will be recorded, known herein as the "Time to Clip";

6. Before leaving the operation room, all participant surgeons and observers will complete the Intra-Operative Case Report Form (Appendices D and E, respectively).

ii. Experimental arm (NIFC) procedures

1. Patient randomized to the experimental arm, at least 45 mins before surgery, will receive a weight-scaled dose of indocyanine green (0.05 mg/kg) by IV and the time of administration and any adverse reactions will be recorded.
2. After inserting the scope in the abdominal cavity, once other standard operatory procedures (e.g., taking down adhesions if necessary, or releasing scar tissue) are completed using white light imaging (WLI) only, the Researcher will record the time when the Calot's triangle is first visualized. From this moment on, the surgery will be recorded.

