Regarding the main secondary outcome, incidence of injuries, the power to detect a drop from 8/1000 in the control arm to 2/1000 in the intervention arm, with a sample size of 500 patients per arm is 15%. Regretfully, with an achievable sample size as the one proposed above, the study will not have enough power to detect a drop in the incidence as important as the one considered.

b. Data Analysis

In general, descriptive statistics including frequencies and means will be used to characterize patient's baseline characteristics in both study arms. Analyses are designed to test the following hypotheses based on the primary objectives: Compared to those in the control arm, surgeons using NIFC will be able to identify a) more frequently the gallbladder cystic union (both before dissection and before clipping); b) a larger number of hepato-biliary structures and; c) more frequently some of the five hepato-biliary structures. We will test the first hypothesis using the chi-square test, the second one using non-parametric test (e.g. Kruskal-Wallis) and the third one using generalized mixed or hierarchical models to account for the clustering induced by the patient.

Multi-center Study Protocol: Efficacy of Near Infrared Incisionless Fluorescent Cholangiography (NIFC) during Laparoscopic Cholecystectomy

Regression models (logistic or generalized mixed models) will be fitted including covariates to evaluate if the effect of NIFC on the primary outcomes is modified by the patient's or surgeon's characteristics and site.

Regarding secondary outcomes we will use the Fisher's exact test or Chi square test (as needed) to compare proportion of patients with bile duct injury, open surgery or bleeding. Time to clipping and time to end of surgery will be compared between arms using the Kruskal-Wallis' test. Regression models will be used when possible -we expect very low incidence of injuries and open surgeries- to evaluate patient's and surgeon's effect modification.

Finally, for those outcomes specific for the NIFC group we will use logistic or generalized linear models to assess whether the reported helpfulness of the NIR light or the reflux maneuver is associated to patient's characteristics or surgeon's experience.

All statistical analysis will be conducted in R software.

14. Anticipated Problems and Solutions

a. Lower than expected Enrollment

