3. AFTER-DISSECTION

A. Document visualization of extra-hepatic biliary anatomy:

For both arms, scope the Calot's triangle area using STD (white-light) mode. If in the NIFC arm, toggle between STD and ICG modes on light source as needed. Check the appropriate boxes below based on what is visible:

	Yes	Maybe	No
Cystic Duct			
Right Hepatic Duct			
Common Hepatic Duct			
Common Bile Duct (CBD)			
Cystic-CBD junction			
Cystic-Gallbladder junction			
Accessory Ducts			

B. For NIFC Arm Only: "Reflux Maneuver" Attempted? Yes No

Repeat the Reflux Maneuver. Check the appropriate boxes based on what is visible:

	Yes	Maybe	No
Cystic Duct			
Cystic-CBD junction			
Cystic-Gallbladder junction			

4. Time to Clip: Time the Cystic Duct was clipped: _____ AM / PM

5. Volume of Bleeding: _____ mL in the bucket/bag or from anesthesia chart at the conclusion of the procedure

6. Bile Leakage: No Yes If yes, Liver bed Other: _____ Did NIFC help identify leak? Yes No

7. Anatomic Anomalies: No Yes If yes, describe: _____

If yes, do you feel NIFC helped you identify this anomaly? Yes No N/A (WLI arm)

8. Was IOC performed? Yes No

9. Were CBD Stones present? Yes No Not Checked

10. Was the procedure converted to Open? Yes No

If yes, explain why: _____

11. Was there a Bile Duct Injury (BDI) during the surgery? Yes No

If yes, complete the BDI Form as described in the Study Protocol.

12. SURGEON FEEDBACK after NIFC:

Did you feel NIFC made your procedure SAFER? Yes No

Were you more CONFIDENT using NIFC vs WLI alone? Yes No

Would you PREFER to use NIFC again vs WLI alone? Yes No

e. Intra-Op Case Report Form – Observer

Near Infrared Incisionless Fluorescent Cholangiography (NIFC)

INTRA-OPERATIVE CASE REPORT FORM - OBSERVER

INSTITUTION: _____

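### Time to Clip has two different end events, clip only or clip-or-conversion, and the analysis has no rule for patients converted to open surgery before clipping

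*Combined protocol and SAP*

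**What the plan says.** Secondary objective 2 (Summary and section 4.b) aims to demonstrate that Time to Clip is reduced with NIFC, and describes it as "defined as the time from the moment Calot's Triangle is first visualized to when the clip is applied". Two data-collection passages use the same end event. Section 9.b.iii has "Time to Clip: Document the time the Cystic Duct was clipped", and item 4 of the surgeon's intra-operative form (Appendix d) asks for "Time the Cystic Duct was clipped".

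Section 12.c differs. Step 5 of the control-arm procedures and step 6 of the NIFC procedures both read "Immediately before clipping or proceeding with open surgery, the total time from Step 1 will be recorded", and both label the result Time to Clip.

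Section 13.b says that time to clipping "will be compared between arms using the Kruskal-Wallis' test". It does not say whether converted patients are censored, excluded or given a particular rank. Conversion is also secondary endpoint 3. Item 10 of the surgeon's form records it as yes or no with a reason, without a time. Section 13.b expects a very low incidence of open surgery but gives no figure. Section 14.b has no rule for an absent clip time.

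**The concern.** A patient converted before clipping has not reached the clip by the time the section 12.c clock stops. Calling that interval Time to Clip mixes two events in one variable, and a rank test cannot tell them apart. An early conversion ranks as a quick result and a late one as a slow result. If conversion rates differ between arms, part of the Time to Clip comparison is then a comparison of conversions.

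The objective is directional: the trial sets out to show that the time is shorter with NIFC. An excess of early conversions under white light would hide part of an NIFC benefit, and an excess of early conversions under NIFC would look like one. Sites may also handle the same situation differently, because section 12.c and the form ask for different things.

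**Working it through.** **The definitions side by side**

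| Place | Clock stops at |
|---|---|
| Objective 2 (Summary, section 4.b) | clip applied |
| Section 9.b.iii | cystic duct clipped |
| Section 12.c, control arm step 5 | clip or conversion |
| Section 12.c, NIFC arm step 6 | clip or conversion |
| Surgeon form, item 4 | cystic duct clipped |
| Surgeon form, item 10 | conversion yes/no and reason; no time |

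Three entries are therefore possible for a patient converted before clipping: the time of conversion (section 12.c), a clip time from the open phase (the form read literally), or a blank. The form does not show whether conversion came before or after clipping.

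**Size of the effect**

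The plan gives no mean, spread, effect or power for Time to Clip, so there is no figure to reproduce. The inputs are 500 patients per arm (section 13.a) and assumed conversion rates a (WLI) and b (NIFC). Assume no true difference in clip time, every conversion before clipping, and every conversion earlier than any clip. With two arms, Kruskal-Wallis is equivalent to the two-sided rank-sum test. Its effect measure is P(NIFC faster), counting ties as one half:

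- As section 12.c is written (conversions at the lowest rank): b(1−a) + ab/2 + (1−a)(1−b)/2 = 0.5 − (a−b)/2.
- If conversions took the worst rank instead: 0.5 + (a−b)/2.
- Standard error under no difference: √[(N+1)/(12·n₁·n₂)] = √[1001/(12·500·500)] = 0.0183.

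| Conversion WLI / NIFC | Shift (a−b)/2 | As written | Worst rank | Shift in SE |
|---|---|---|---|---|
| 1% / 0.5% | 0.0025 | 0.4975 | 0.5025 | 0.14 |
| 2% / 1% | 0.005 | 0.495 | 0.505 | 0.27 |
| 3% / 1% | 0.01 | 0.49 | 0.51 | 0.55 |
| 5% / 1% | 0.02 | 0.48 | 0.52 | 1.1 |

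**Check by simulation**

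The simulation used 1,000 runs per setting, 500 per arm, and a two-sided 5% test. Clip times were assumed lognormal with median 20 minutes and log-SD 0.5, with no true difference. Conversion times were spread around a multiple of the median clip time.

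- Early conversion (0.25 × median): P(NIFC faster) as written was 0.497, 0.496, 0.484 and 0.475 at 1%/0.5%, 2%/1%, 5%/2% and 10%/5%. With worst rank it was 0.503, 0.506, 0.514 and 0.524.
- In the same settings, a significant result favouring WLI, the arm with more conversions, occurred in 4.1%, 3.4%, 14.2% and 27.7% of runs, against a nominal 2.5%. The simulation error at 2.5% is about √(0.025·0.975/1000) = 0.5 percentage points, so the first two settings show only a small excess.
- Late conversion (1.5 × median): P(NIFC faster) as written was 0.501, 0.503, 0.505 and 0.511. The direction reverses and now favours the arm with fewer conversions.

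**The case against.** The strongest reply accepts the wording conflict but disputes that it does harm. Data reach the database through the case report forms, and the only Time to Clip field asks for the time of clipping. Section 13.b likewise speaks of time to clipping. A conversion time has no field of its own, so it may never enter the analysis, and the practical result may be a missing or open-phase value. Surgery is recorded from the first view of Calot's triangle, so the end of the laparoscopic phase may be recoverable. The section 12.c rule is the same in both arms, so it distorts the comparison only if conversions differ between arms in number or timing. The endpoint is secondary and unpowered. Worst-rank scoring is itself a choice: it combines time with conversion, which already has its own endpoint and test.

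Most of this stands, and it limits the size of the point and leaves the choice of analysis rule open. It does not remove the contradiction. Section 12.c is the operative procedure text, and followed as written it records a conversion time as a clip time. A blank or an open-phase time also needs a rule, and there is none.

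A reader might infer that the plan systematically rewards failed laparoscopy, or that the rule would reverse the trial's finding on this endpoint. The documents do not support that. They do not say when conversions occur, and late ones push the other way. The reversal in the table is a movement around no difference, of at most 1.1 standard errors even at 5% versus 1%.

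**Conclusion.** The definition is wrong as written: one endpoint has two end events, and nothing says how patients converted before clipping are analysed. That conclusion rests on the text alone and is firm.

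The size is conditional. With all conversions early and 500 per arm, the shift is 0.14 to 0.27 standard errors at WLI conversion of 1% to 2% with half that rate under NIFC. It becomes noticeable only at rates such as 5% or more, which do not fit the plan's expectation of very rare open surgery. The direction depends on which arm has more conversions and how early they occur. All conversion rates and timings here are assumptions.

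This is a minor-to-moderate point on a secondary endpoint, worth correcting before data are seen. It is separate from the conflict over the start of the clock. Section 12.c counts from Step 1, which is the first view of Calot's triangle in the control arm but the dye injection, at least 45 minutes before surgery, in the NIFC arm. Those passages must also be reconciled, and read literally that discrepancy would far outweigh this one.

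**What to change.** 1. Use one end event, the clip being applied, in objective 2, section 9.b.iii, both procedures in section 12.c and the surgeon's form. In practice this means removing the conversion alternative from control-arm step 5 and NIFC step 6.
2. Add a field to the surgeon's form for the time of conversion and whether it preceded clipping.
3. State in section 13.b, before data are seen, how patients converted before clipping enter the between-arm comparison. Worst rank is one defensible choice; treating conversion as a competing event is another. Report the non-converted patients as a sensitivity analysis.

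The cost is protocol and SAP wording plus a short addition to one form. Under worst rank no mean can be quoted for Time to Clip, and the median shifts slightly with the conversion rate. With 5% converted, the arm median sits at 0.50/0.95, about the 53rd percentile of actual clip times. With conversions at the lowest rank it sits at 0.45/0.95, about the 47th.
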